7.8.4 Analysis

All PK parameters will be listed for all subjects providing PK data. All analyses will be conducted on the PKS.

For mean value calculations, all values below the limit of quantification (BLQ) will be set to zero. If > 50% of the values at a given time point are BLQ, no mean value will be calculated. Mean concentration-time profiles will be generated using these criteria.

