10.2.4 Pharmacokinetic variables

Plasma PK parameters of selexipag and its active metabolite, ACT-333679, will be derived by non-compartmental analysis of the concentration-time profiles. The PK parameters will be calculated on the basis of the real blood sampling time points (in relation to the last selexipag intake during each period).

The measured individual plasma concentrations of selexipag will be used to directly obtain $C_{trough, ss}$, $C_{max, ss}$, and $t_{max, ss}$.

$AUC_{\tau, ss}$ will be calculated according to the linear trapezoidal rule using the measured concentration-time values above the LOQ during one dosing interval at steady state.

For mean value calculations, all values below the limit of quantification (BLQ) will be set to zero. If > 50% of the values at a given time point are BLQ, no mean value will be calculated. Mean concentration-time profiles will be generated using these criteria.

$C_{max, ss}$, $C_{trough, ss}$, and $AUC_{\tau, ss}$, values are assumed to be log-normally distributed [Julious 2000].

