7.8.3 Pharmacokinetic variables

Plasma PK parameters of selexipag and its active metabolite, ACT-333679, will be derived by non-compartmental analysis of the concentration-time profiles.

The PK parameters will be calculated on the basis of the real blood sampling time points (in relation to the last selexipag intake during each period).

The measured individual plasma concentrations of selexipag will be used to directly obtain $C_{trough, ss}$, $C_{max, ss}$, and $t_{max, ss}$.

$AUC_{\tau, ss}$ will be calculated according to the linear trapezoidal rule using the measured concentration-time values above the limit of quantification (LOQ) during one dosing interval at steady state.

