7.8.4.2 Trough concentrations

Selexipag and ACT-333679 $C_{\text{trough, ss}}$ will be listed by dose, subject, and period as well as the ratio of the periods per subject.

Summary statistics will be provided by dose, including dose normalized, and by period. Implausible $C_{\text{trough, ss}}$ values will be flagged in the listings and not included in summary statistics.

7.8.4.3 $C_{\text{max, ss}}$, $t_{\text{max, ss}}$, and $AUC_{\tau, ss}$

$C_{\text{max, ss}}$, $t_{\text{max, ss}}$, and $AUC_{\tau, ss}$ of selexipag and ACT-333679 will be listed by dose, subject, and period. The ratio of the parameters between i.v. selexipag (test treatment) and Uptravi (reference treatment) per subject will be shown, except for $t_{\text{max, ss}}$. Any values

obtained from implausible plasma concentrations of selexipag or ACT-333679 will be flagged in the listings and not included in the statistical analysis.

Summary statistics will be provided by dose and period for selexipag and ACT-333679.

Dose-normalized $C_{max, ss}$ and $AUC_{\tau, ss}$ will be listed and summarized by period as well for selexipag and ACT-333679.

$C_{max, ss}$ and $AUC_{\tau, ss}$ ratio of ACT-333679/selexipag will be listed by dose, subject, and treatment and will be summarized by dose and treatment.

The ratio of $C_{max, ss}$ and $AUC_{\tau, ss}$ of selexipag and ACT-333679 between Uptravi and i.v. selexipag, after dose normalization, within each dose level (if sufficient subjects are enrolled per level) will be estimated by fitting a mixed effect model to the data using period (i.e., treatment) as fixed, and subject as random effect to the log-transformed $C_{max, ss}$ and $AUC_{\tau, ss}$ values. The ratios of geometric means between i.v. selexipag (test treatment) and Uptravi (reference treatment) will be computed and displayed together with their 90% CI by back-transforming the period contrasts and interval boundaries of the log-transformed data. If dose-proportionality is shown within each dose, then an overall model may be considered for robustness.

The inter-subject coefficient of variation (CV_b) of $C_{max, ss}$ and $AUC_{\tau, ss}$ of selexipag and ACT-333679 will be computed by using the mean squared error (MSE) of the mixed model as an estimate of variation.

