8.1.2 Summary statistics of PK data

PK data will be listed as described in Section 7.8.4 and summarized using appropriate descriptive statistics:

- Plasma concentrations of selexipag and ACT-333679 will be summarized using number of non-missing observations, arithmetic mean, geometric mean, standard deviation (SD), standard error of the mean (SE), minimum, median, maximum and 95% CIs for the arithmetic and geometric mean.
- $C_{trough, ss}$ of selexipag and ACT-333679 will be summarized using number of non-missing observations, arithmetic mean, geometric mean, SD, SE, coefficient of variation of the observed and logarithmized data (CV, CV_{ln}) in %, minimum, median, maximum and 95% CIs for the arithmetic and geometric mean.
- $C_{max, ss}$ and $AUC_{\tau, ss}$ of selexipag and ACT-333679 will be summarized using number of non-missing observations, arithmetic mean, geometric mean, SD, SE, CV%, $CV_{ln}\%$, minimum, median, maximum, 95% CIs for the arithmetic and geometric mean.
- $t_{max, ss}$ of selexipag and ACT-333679 will be summarized using number of non-missing observations, arithmetic mean, SD, SE, CV%, minimum, median, maximum and 95% CI for the arithmetic mean.

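### Values below the LOQ are dropped from AUC and enter geometric means as zeros; parent selexipag results suffer if troughs fall below the LOQ

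*SAP*

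**What the plan says.** **Means.** SAP 7.8.4: for mean calculations "all values below the limit of quantification (BLQ) will be set to zero". It adds: "If > 50% of the values at a given time point are BLQ, no mean value will be calculated". Protocol 10.2.4 has the same two rules.

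**AUC.** SAP 7.8.3 applies the linear trapezoidal rule "using the measured concentration-time values above the limit of quantification (LOQ) during one dosing interval at steady state". Protocol 10.2.4 agrees: "using the measured concentration-time values above the LOQ during one dosing interval at steady state".

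**Log-scale summaries.** Under SAP 8.1.2, concentrations and Ctrough "will be summarized using number of non-missing observations, arithmetic mean, geometric mean", with 95% CIs for both means and, for Ctrough, the CV of the log data. SAP 8.2 assumes log-normality for Ctrough, Cmax and AUC.

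**Trough ratio.** SAP 7.8.4.2 says troughs "will be listed by dose, subject, and period as well as the ratio of the periods per subject". SAP 11.3.2 names this ratio as an addition to the protocol.

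Neither document says how a zero enters a geometric mean, how a ratio with a BLQ value is shown, or what happens when the first or last sample of the interval is BLQ. The implausible-value rules and the deviation codes that exclude data from the PKS do not cover BLQ.

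**The concern.** There are two separate faults.

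1. **AUC.** Dropping a point inside the curve only joins its neighbours. Dropping the first or last point removes area. The oral grid starts 0, 1 h and the i.v. grid 0, 25 min (protocol 7.2.5.1.1), so the lost first segments differ in length. They also differ in share of the total, so the loss does not cancel in the i.v./oral ratio. That ratio for parent selexipag is marked as a key deliverable (PK_MM_SEL, SAP 12.8). The ACT-333679/selexipag AUC ratio has the same parent AUC as its denominator.

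2. **Geometric means.** Zero has no logarithm. One BLQ value gives a geometric mean of zero or, if the software discards log(0), a mean over quantifiable subjects only, which is too high. The 50% rule does not prevent this. Group A has 5 to 8 subjects who may spread over five dose levels, and summaries are by dose. With two subjects at a level, one BLQ value is exactly 50%, so a mean is still produced.

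**Working it through.** The plan attaches no figure to these rules, so there is none to reproduce.

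**Inputs from the documents**
- LOQ 0.01 ng/mL for both analytes (protocol 7.2.5.1.3).
- Parent AUC 11.04 h·ng/mL after 400 µg oral and 11.16 after 200 µg i.v. (protocol 1.2.4). Assuming dose proportionality, 200 µg oral gives A = 11.04 × 200/400 = 5.52 and 225 µg i.v. gives A = 11.16 × 225/200 = 12.555.
- Sampling: oral 0, 1, 2, 4, 6, 8, 12 h; i.v. 0, 25 min, 87 min, 4, 6, 8, 12 h.
- Infusion: 5 of 50 mL over 15 min, then 45 of 50 mL over 72 min (protocol 5.1.4).

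**Assumed, because not in the documents:** half-life 0.7-1.5 h, ka 0.6-3 per h, one compartment at steady state. k = ln 2 / half-life.

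**Formulas**
- Oral: C(t) = A·k·ka/(ka − k) × [e^(−kt)/(1 − e^(−12k)) − e^(−ka·t)/(1 − e^(−12ka))].
- i.v.: each part delivers fraction f of the dose from time a to b. During it C = f·A/(b − a) × (1 − e^(−k(t−a))); afterwards C = f·A/(b − a) × (1 − e^(−k(b−a))) × e^(−k(t−b)). Both parts are summed over doses 12 h apart.
- AUC by linear trapezoid, comparing BLQ entered as 0 with BLQ dropped.

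Dose normalization does not alter the comparison. Oral values are multiplied by 200/D and i.v. values by 225/(1.125·D) = 200/D, which cancels in the ratio.

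**One case in full** (200/225 µg, half-life 1 h, ka 1.5; both troughs BLQ, at 0.0017 and 0.0038 ng/mL)
- Oral: first segment 1 × 1.970/2 = 0.985; last segment 4 × 0.0277/2 = 0.055. AUC falls from 5.265 to 4.224, a loss of 19.8%.
- i.v.: first segment (25/60) × 1.742/2 = 0.363; last segment 4 × 0.0605/2 = 0.121. AUC falls from 14.283 to 13.799, a loss of 3.4%.
- Ratio: 14.283/5.265 = 2.713 becomes 13.799/4.224 = 3.267, a factor of 1.204.

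**Across assumptions**

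| Oral/i.v. µg | Half-life (h) | ka (per h) | Oral trough (ng/mL) | Oral loss | i.v. loss | Ratio factor |
|---|---|---|---|---|---|---|
| 200/225 | 0.7 | 3 | 0.00006 | 29% | 3% | 1.357 |
| 200/225 | 0.8 | 0.6 | 0.0077 | 16% | 3% | 1.149 |
| 200/225 | 1.2 | 1 | 0.0073 | 16% | 0% | 1.195 |
| 200/225 | 1.0 | 0.6 | 0.0124 | 0% | 3% | 0.966 |
| 200/225 | 1.5 | 0.6-3 | 0.012-0.035 | 0% | 0% | 1.000 |
| 1600/1800 | 0.8 | 1-3 | 0.0016-0.0070 | 19-26% | 3% | 1.188-1.315 |
| 1600/1800 | 1.0 | 1.5 | 0.0139 | 0% | 0% | 1.000 |

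The first two rows are the extremes among the 200 µg profiles with a BLQ oral trough.

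**Geometric mean, invented troughs** 0.03, 0.02, 0.015 ng/mL and one BLQ (25%, so a mean is printed)
- BLQ as 0: zero or undefined.
- log(0) discarded: (0.03 × 0.02 × 0.015)^(1/3) = 0.0208.
- LOQ/2 = 0.005: (0.03 × 0.02 × 0.015 × 0.005)^(1/4) = 0.0146.

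The arithmetic mean barely depends on the choice: 0.0163 with zero, 0.0175 with LOQ/2.

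**The case against.** The strongest case against is that this may never happen. The documents give no half-life, ka or BLQ frequency, and much of the plausible range shows nothing. At half-life 1.5 h every modelled trough is quantifiable. At half-life 1 h, 1600 µg profiles stay quantifiable except at the fastest absorption (0.0097 ng/mL at ka 3). Group B (1200-1600 µg) supplies 12 to 15 of about 20 subjects. Sparse dose levels get a modelled ratio only if enough subjects are present, and the study is descriptive with a safety objective. All of this stands, and it limits the likelihood and weight of the point. It does not remove it: at half-life 0.8 h with ka 1-3 the highest dose is affected too, and the pooled dose-normalized ratio includes every dose level.

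Non-compartmental software may insert a value at time zero. Neither document says it will, so the result would depend on a default.

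Two stronger readings are not supported. A reader might infer that the exposure match itself is biased. Matching is on ACT-333679, whose oral AUC is 37.97/11.04 = 3.44 times the parent's with the same LOQ, and no effect has been shown for it. A reader might also infer that the i.v./oral trough ratio is biased by division by zero. The zero rule covers means only, and the ratio is listed and not modelled. What is missing there is a display rule.

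**Conclusion.** The point holds as a conditional defect in the parent selexipag analysis. Read literally, the AUC rule removes real area whenever an end sample is BLQ. The zero rule cannot be combined with the log-scale summaries the SAP requires.

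If the oral pre-dose sample at 200 µg is BLQ, the parent i.v./oral AUC ratio is inflated about 1.15- to 1.36-fold. If only the i.v. trough is BLQ, the ratio falls about 3%. If neither is BLQ, nothing changes. These sizes rest on a one-compartment model, dose proportionality, and assumed half-life and ka. The direction does not run one way, so an upward bias should not be presumed.

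The point does not touch the primary safety objective. It is worth correcting because the fix costs little and the choice would otherwise fall to software defaults or be made after the data are seen.

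**What to change.** State one BLQ rule for each use, before database lock:

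- **AUC:** enter BLQ values at pre-dose and at 12 h as 0 and keep them in the trapezoid. The error is at most 0.01 × 1/2 = 0.005 h·ng/mL for the oral first segment and 0.01 × 4/2 = 0.02 h·ng/mL for the 8-12 h segment. Against 5.52 h·ng/mL at 200 µg oral that is about 0.1% and 0.4%.
- **Arithmetic means:** keep zero.
- **Geometric means, log-scale CIs and CVln:** use LOQ/2 (0.005 ng/mL), print the number BLQ, and keep the existing rule that suppresses means above 50% BLQ.
- **Per-subject trough ratios:** show any ratio involving a BLQ value as not calculable in the listing.

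The AUC and mean rules also stand in protocol 10.2.4, so SAP 11.1, which now reports no changes, needs an entry. The cost is a few sentences and minor programming. The downside is that LOQ/2 is a convention, and printing the BLQ count lets readers judge its influence.

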7.8.4.1 Plasma concentrations

The PK expert will examine the plasma concentration data and identify implausible values.

Plasma concentrations of selexipag and ACT-333679 will be listed per subject, time point, and period (i.e., for Uptravi and i.v. selexipag). Implausible plasma concentrations of selexipag or ACT-333679 will be flagged in the listings.

Plasma concentrations of selexipag and ACT-333679 will be summarized per time point by dose, including dose normalized, and period (i.e., for Uptravi and i.v. selexipag). Implausible plasma concentrations of selexipag or ACT-333679 will not be included in the summary statistics.

Implausible values will be indicated in the comments value variable (COVAL) of the comments dataset (CO). The reference link (COREF) will be used to join these implausible values with time points of the plasma concentration dataset (PC).

7.8.4.2 Trough concentrations

Selexipag and ACT-333679 $C_{\text{trough, ss}}$ will be listed by dose, subject, and period as well as the ratio of the periods per subject.

Summary statistics will be provided by dose, including dose normalized, and by period. Implausible $C_{\text{trough, ss}}$ values will be flagged in the listings and not included in summary statistics.

7.8.4.3 $C_{\text{max, ss}}$, $t_{\text{max, ss}}$, and $AUC_{\tau, ss}$

$C_{\text{max, ss}}$, $t_{\text{max, ss}}$, and $AUC_{\tau, ss}$ of selexipag and ACT-333679 will be listed by dose, subject, and period. The ratio of the parameters between i.v. selexipag (test treatment) and Uptravi (reference treatment) per subject will be shown, except for $t_{\text{max, ss}}$. Any values

obtained from implausible plasma concentrations of selexipag or ACT-333679 will be flagged in the listings and not included in the statistical analysis.

Summary statistics will be provided by dose and period for selexipag and ACT-333679.

Dose-normalized $C_{max, ss}$ and $AUC_{\tau, ss}$ will be listed and summarized by period as well for selexipag and ACT-333679.

$C_{max, ss}$ and $AUC_{\tau, ss}$ ratio of ACT-333679/selexipag will be listed by dose, subject, and treatment and will be summarized by dose and treatment.

The ratio of $C_{max, ss}$ and $AUC_{\tau, ss}$ of selexipag and ACT-333679 between Uptravi and i.v. selexipag, after dose normalization, within each dose level (if sufficient subjects are enrolled per level) will be estimated by fitting a mixed effect model to the data using period (i.e., treatment) as fixed, and subject as random effect to the log-transformed $C_{max, ss}$ and $AUC_{\tau, ss}$ values. The ratios of geometric means between i.v. selexipag (test treatment) and Uptravi (reference treatment) will be computed and displayed together with their 90% CI by back-transforming the period contrasts and interval boundaries of the log-transformed data. If dose-proportionality is shown within each dose, then an overall model may be considered for robustness.

The inter-subject coefficient of variation (CV_b) of $C_{max, ss}$ and $AUC_{\tau, ss}$ of selexipag and ACT-333679 will be computed by using the mean squared error (MSE) of the mixed model as an estimate of variation.

Based on the previous studies QGUY/2006/NS304/-01, AC-065-101 and AC-065A201 it is known that the PK profile of selexipag and its active metabolite ACT-333679 is dose-proportional up to a single dose of 800 ug and for multiple doses of up to 1800 ug b.i.d. after oral administration.

Dose proportionality of $AUC_{\tau, ss}$ of selexipag and ACT-333679 after i.v. selexipag will be analyzed using the power model approach [Gough 1995], if at least three different dose levels with a sufficient number of subjects to compute CIs are included in the PKS. A plot of log dose versus log $AUC_{\tau, ss}$ including the slope of the estimated parameter will be displayed.

Differences in $t_{max, ss}$ of ACT-333679 between the i.v. selexipag period and the Uptravi period will be assessed within each dose level using a Wilcoxon signed rank test and displaying the median estimate and exact 90% CI of the location shift using Hodges-Lehmann estimation.

If considered appropriate, a sensitivity analysis may be conducted to evaluate the statistical impact of the plasma concentrations of selexipag or ACT-333679 that were considered implausible by the PK expert.

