5.1.8.2 Study treatment compliance

Study treatment compliance is a measure of how closely the protocol instructions for administering i.v. selexipag were adhered to.

The compliance will be calculated as the percentage of the actual dose infused compared with the targeted dose to be infused.

Over the entire treatment period, compliance is expected to be between 80% and 120% otherwise it will be considered to be a protocol deviation and reported as such. The investigator must document in the subject's source notes the reasons for this protocol deviation.

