10.3.5 Analysis of PK variables

For all PK analyses, the Pharmacokinetic Analysis Set will be employed.

- Plasma concentrations of selexipag and ACT-333679 will be summarized per time point by dose and period using arithmetic mean, geometric mean, minimum, median,

maximum, standard deviation (SD), standard error (SE), and two-sided 95% CI of the means.

- $C_{trough, ss}$ of selexipag and ACT-333679 will be listed by dose, period and subject, and will be summarized by dose and period using arithmetic mean, geometric mean, minimum, median, maximum, SD, SE, and coefficients of variation (CV, CV_{ln}) in %, and two-sided 95% CI of the means.
- $C_{max, ss}$, $t_{max, ss}$, and $AUC_{\tau, ss}$ of selexipag and ACT-333679 will be listed by dose, period, and subject.
- $C_{max, ss}$, $t_{max, ss}^*$ and $AUC_{\tau, ss}$, will be summarized by dose and period with arithmetic mean, geometric mean, minimum, median, maximum, SD, SE, $CV\%$ and $CV_{ln}\%$, 95% CI of the arithmetic and geometric means, and inter-subject coefficient of variation (CV_b). (* For $t_{max, ss}$, the geometric mean, its 95% CI and CV_{ln} will not be calculated).
- Differences in $C_{max, ss}$ and $AUC_{\tau, ss}$ of selexipag and ACT-333679 between periods will be explored after dose normalization and within each dose level by using the 90% CI of the ratio of the geometric means of selexipag i.v. (test treatment) versus selexipag oral (reference treatment). The log-transformed values will be analyzed by mixed-effect models including treatment and period as fixed effects and subject as random effect. The ratios of geometric means and their 90% CI will be calculated from the corresponding back log-transformed contrasts of the mixed-effects models for $C_{max, ss}$ and $AUC_{\tau, ss}$ of selexipag and ACT-333679 after oral or i.v. selexipag administration.
- Differences for $t_{max, ss}$ of ACT-333679 between periods will be explored within each dose level using the Wilcoxon signed rank test providing the median differences and their 90% CI.
- Dose proportionality for $AUC_{\tau, ss}$ of selexipag and ACT-333679 after selexipag i.v. will be explored by the power model as described by [Gough 1995], (this analysis will only be done if there are at least 3 different doses in the study).
- $C_{max, ss}$ and $AUC_{\tau, ss}$ ratio of ACT-333679 / selexipag will be listed by dose, period, and subject and will be summarized by dose and period.

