7.8.3.1 Dose normalization

Dose normalization will be conducted to the lowest prescribed selexipag dose (200 µg for oral Uptravi and 225 µg for i.v. selexipag).

Dose normalized plasma concentrations, $C_{\text{trough, ss, norm}}$, $C_{\text{max, ss, norm}}$ and $AUC_{\tau, ss, \text{norm}}$ will be determined by dividing the respective parameters by the actual dose and multiplying with 200 or 225 for Uptravi and i.v. selexipag parameters, respectively.

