8.2.2 Statistical methods for continuous data

8.2.2.1 *Differences between periods in $C_{max, ss}$ and $AUC_{\tau, ss}$ of selexipag/ACT-333679*

Within each dose level and after dose normalization, differences between the Utravi and i.v. selexipag periods will be analyzed by computing the geometric mean ratios of the respective period with the oral formulation as reference treatment in the denominator. This is done by fitting a mixed linear model to the log-transformed $C_{max, ss}$ and $AUC_{\tau, ss}$ values with period as fixed and subject as random effect. The Kenward-Rodgers method for calculation of degrees of freedom will be used to obtain degrees of freedom to calculate CIs. An unstructured covariance matrix will be assumed. The difference of the least squares mean and its 90% CI will be computed and transformed back to normal scale to obtain the geometric mean ratio. SAS® code similar to the code shown below will be used:

```
PROC MIXED data=<input_dataset>;
CLASS period;
MODEL log_response=period / DDFM=KR;
RANDOM intercept /subject=usubjid TYPE=UN;
ESTIMATE 'Difference i.v. - oral' period -1 1 /CL ALPHA=0.1;
RUN;
```

8.2.2.2 *CV_b in C_{max, ss} and AUC_{t, ss} of selexipag/ACT-333679*

The CV_b expressed in percent will be computed using the formula

$$CV_b [\%] = 100\sqrt{e^{S_b^2} - 1}$$

where S_b² is the MSE of the residuals from the mixed effects model described in Section 8.2.2.1.

8.2.2.3 *Dose proportionality of AUC_{t, ss} of selexipag/ACT-333679*

To assess dose proportionality of selexipag the power model approach will be used:

The power model approach specifies a relationship between the scheduled dose D of i.v. selexipag and AUC_{t, ss} of selexipag / ACT-333679 which is expressed as

$$Y_{ij} = \alpha_j' * D_i^\beta * \varepsilon'_{ij}$$

Together with α' denoting $\exp(\alpha)$ and ε'_{ij} denoting $\exp(\varepsilon'_{ij})$, logarithmizing both sides of the equation yields a linear model

$$\log(Y_{ij}) = \alpha_j + \beta \log(D_i) + \varepsilon_{ij}$$

with

Y_{ij} AUC_{τ, ss} of dose level i in subject j (i=1, ..., I), (j=1, ..., n)

α_j intercept parameter (assumed to be a random effect)

β the slope parameter

D_i size of dose level i

ε_{ij} random error term of subject j in dose level i.

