Output: <Output name>, Produced by DATAMAP on ddMMMyyyy hh:mm (CET),

SDTM Date: ddMMMyyyy

Program: /<folder>/<program name>.sas

Page x of y

Programming note: Continue for dose all dose levels and dose normalized.

T PK RATIO SUM

ACT-293987

Protocol: AC-065A309

Summary of PK parameters of ratio ACT-333679/selexipag concentration by dose level and treatment Analysis Set: Pharmacokinetic Analysis Set

Dose level: 200 ug b.i.d. p.o./ 225 ug b.i.d. i.v.

PK parameter Statistic	Uptravi N=xxx	i.v. selexipag N=xxx
Subjects in dose level	xxx	xxx
AUCtau,ss [ng.h/mL]		
N	xxx	xxx
Arithmetic mean (95% CI)	xxx (xx.xx, xx.xx)	xxx (xx.xx, xx.xx)
Geometric mean (95% CI)	xxx (xx.xx, xx.xx)	xxx (xx.xx, xx.xx)
SD	xx.xxxx	xx.xxxx
SE	xx.xxxx	xx.xxxx
CV%	xx.xx	xx.xx
CV ln%	xx.xx	xx.xx
Median	xx.xx	xx.xx
Min, Max	xx.xx, xx.xx	xx.xx, xx.xx
Cmax,ss [ng/mL]		
n	xxx	xxx
Arithmetic mean (95% CI)	xxx (xx.xx, xx.xx)	xxx (xx.xx, xx.xx)
Geometric mean (95% CI)	xxx (xx.xx, xx.xx)	xxx (xx.xx, xx.xx)
SD	xx.xxxx	xx.xxxx
SE	xx.xxxx	xx.xxxx
CV%	xx.xx	xx.xx
CV ln%	xx.xx	xx.xx
Median	xx.xx	xx.xx
Min, Max	xx.xx, xx.xx	xx.xx, xx.xx

CI = Confidence interval, SD = Standard deviation, SE = Standard error, CV% = Coefficient of variation (SD/mean) [%], CV_ln% = Coefficient of variation of logarithmized values, [%] p.o. = per os, b.i.d. = twice daily; i.v.= intravenous

Values obtained from implausible plasma concentrations are not included in the summary.

Output: <Output name>, Produced by DATAMAP on ddMMMyyyy hh:mm (CET),

SDTM Date: ddMMMyyyy

Program: /<folder>/<program_name>.sas

Page x of y

Programming note: Continue for dose all dose levels and dose normalized.

T_PK_MM

ACT-293987

Protocol: AC-065A309

Mixed model analysis: Ratio of Uptravi and i.v. selexipag period for <selexipag/ACT-333679> by dose level

Analysis Set: Pharmacokinetic Analysis Set

Endpoint Statistic	Cmax,ss	AUCtau ss
Dose level: 200 ug b.i.d. p.o./ 225 ug b.i.d. i.v.		
n	xxx	xxx
Ratio of geom. means (i.v./p.o)	x.xx (x.xx, x.xx)	x.xx (x.xx, x.xx)
90% CI	x.xxxx, x.xxxx	x.xxxx, x.xxxx
CV b[%]	xx.xx	xx.xx
Dose level: 400 ug b.i.d. p.o./ 450 ug b.i.d. i.v.		
n	xxx	xxx
Ratio of geom. means (i.v./p.o)	xxx (xx.x, xx.x)	xxx (xx.x, xx.x)
90% CI	x.xxxx, x.xxxx	x.xxxx, x.xxxx
CV b[%]	xx.x	xx.x
Dose level: ...		
n	xxx	xxx
Ratio of geom. means (i.v./p.o)	xxx (xx.x, xx.x)	xxx (xx.x, xx.x)
90% CI	x.xxxx, x.xxxx	x.xxxx, x.xxxx
CV b[%]	xx.x	xx.x
...		
Dose level: Normalized dose (200 ug)		
n	xxx	xxx

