Ratio of geom. means (i.v./p.o)	xxx (xx.x, xx.x)	xxx (xx.x, xx.x)
90% CI	x.xxxx, x.xxxx	x.xxxx, x.xxxx
CV b[%]	xx.x	xx.x
CI = Confidence interval, n.e. = not estimable. p.o. = per os, b.i.d. = twice daily; i.v. = intravenous		
Geometric mean ratios were obtained by computing the anti-log of the treatment group difference of a mixed model with treatment as fixed and subject as random effect to the log-transformed data. CV_b[%] was computed using the mean squared error of residuals as a measure of variation. Values obtained from implausible plasma concentrations are not included in the analysis.		
Output: <Output name>, Produced by DATAMAP on ddMMMyyyy hh:mm (CET),		
SDTM Date: ddMMMyyyy		
Program: /<folder>/<program_name>.sas		
Page x of y		

Programming note: Display all dose levels. For dose levels not sufficiently populated to allow an estimation populate only 'n' row and show 'n.e.' for the remaining statistics.

T_PK_POW

ACT-293987

Protocol: AC-065A309

Dose proportionality of AUCtau of <selexipag/ACT-333679> after i.v. selexipag: Power model estimation

Analysis Set: Pharmacokinetic Analysis Set

n	beta	SE(beta)	90% CI
xxx	x.xxx	xx.xxxx	x.xxxx, x.xxx

CI = Confidence interval

Dose proportionality will be assumed if beta is close to 1, i.e., if the CI of beta includes 1.

Values obtained from implausible plasma concentrations are not included in the analysis.

Output: <Output name>, Produced by DATAMAP on ddMMMyyyy hh:mm (CET),

SDTM Date: ddMMMyyyy

Program: /<folder>/<program_name>.sas

Page x of y

Programming note: Produce table only if sufficient subjects are included in at least three dose levels.

T_PK_WIL

ACT-293987

Protocol: AC-065A309

Location shift analysis of tmax, ss of <selexipag/ACT-333679>

Analysis Set: Pharmacokinetic Analysis Set

n	i.v. selexipag - Uptravi Median	90% CI	p-value
xxx	x.xxx	x.xxxx, x.xxx	x.xxxx

CI = Confidence interval from a Hodges - Lehmann estimation.

p-value is derived from a Wilcoxon signed rank test.

Values obtained from implausible plasma concentrations are not included in the analysis.

Output: <Output name>, Produced by DATAMAP on ddMMMyyyy hh:mm (CET),

SDTM Date: ddMMMyyyy

Program: /<folder>/<program_name>.sas

Page x of y

[figure not shown]
F EXP

ACT-293987

Protocol: AC-065A309

Shift in selexipag dose between oral and i.v. treatment

Analysis Set: i.v. Safety Analysis Set

Output: <Output name>, Produced by DATAMAP on ddMMyyyy hh:mm (CET),

SDTM Date: ddMMyyyy

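### Three descriptive PK rules in the SAP do not work as written: the condition on the pooled i.v./oral model, the per-level exact t_max interval, and the proportionality footnote

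*SAP*

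**What the plan says.** **Pooled ratio.** Protocol 10.3.5 says that differences in Cmax,ss and AUCtau,ss "will be explored after dose normalization and within each dose level by using the 90% CI of the ratio of the geometric means". SAP 8.2.2.1 opens in the same way ("Within each dose level and after dose normalization"), and its sample code, "MODEL log_response=period / DDFM=KR", has no dose-level term or BY statement. SAP 7.8.4.3 plans the ratio at each dose level if enough subjects are enrolled there, gives no number, and then adds: "If dose-proportionality is shown within each dose, then an overall model may be considered for robustness". Shell T_PK_MM in Appendix E, a key deliverable in SAP 12.8, lists the dose levels and ends with a row headed "Dose level: Normalized dose (200 ug". Its programming note sets one limit only: "For dose levels not sufficiently populated to allow an estimation populate only 'n' row and show 'n.e.' for the remaining statistics". SAP 7.8.3.1 normalises by "dividing the respective parameters by the actual dose and multiplying with 200 or 225 for Uptravi and i.v. selexipag parameters, respectively".

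**t_max.** SAP 7.8.4.3 plans a signed-rank test at each dose level with an exact 90% interval for the shift. SAP 8.2.2.4 qualifies this only by computational feasibility. Shell T_PK_WIL has one row and no dose levels.

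**Proportionality.** SAP 7.8.4.3 takes oral PK as dose-proportional from previous studies, for multiple doses up to 1800 µg b.i.d. It plans a power model for AUCtau,ss after i.v. dosing only. The T_PK_POW footnote says proportionality will be assumed when the CI of the slope includes 1. SAP 8.2.2.3 says only that 1 should lie in the 90% CI if proportionality holds.

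**The concern.** Each rule tells the programmer or author to do something that cannot be done or that the data would not support.

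The condition on the pooled model cannot be evaluated, and text and shell disagree on whether the model is run. This matters because 18 subjects over eight levels average 2.25 per level, so the pooled ratio is the only precise summary of the comparable-exposure premise in the primary objective.

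The t_max text promises an interval that does not exist at most levels. The footnote lets a wide interval count as evidence for proportionality, in tables that are key deliverables.

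**Working it through.** **The plan's own figures.** The only sample-size figures are the 95% Clopper-Pearson upper limits. They reproduce: 2/18 gives 34.7% (plan: 35%) and 2/20 gives 31.7% (plan: 32%). There is no precision figure for PK.

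**1. Pooled model.**

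*Normalisation.* In SAP Table 6 every pair has the same ratio, from 225/200 = 1.125 to 1800/1600 = 1.125. So 200/oral dose = 225/i.v. dose at every level, and at planned doses normalisation cancels from the within-subject ratio. In a simulation with slope 0.5 by both routes, the pooled model returned a ratio of 1.000 with 89.9% coverage, so proportionality as such is not required.

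*What is required.* The i.v./oral ratio must be constant across doses. With oral slope 1 and i.v. slope b, it changes over the eight-fold range by 8^(b−1). At b = 0.7 this is 8^(−0.3) = 0.54, which one pooled figure would hide. Since the SAP takes the oral slope as 1, the i.v. power-model slope is informative about constancy for AUC. No equivalent analysis is planned for Cmax,ss.

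*Actual doses.* Protocol 5.1.8.2: "Over the entire treatment period, compliance is expected to be between 80% and 120"%. At r = 0.8 or 1.2 of the planned dose, one subject's normalised ratio shifts by r^(b−1). At b = 0.7 this is 1.07 or 0.95; at b = 0.8 it is 1.05 or 0.96. This effect is small.

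*Precision.* The 90% CI factor is exp(t(0.95, n−1) × √2 × s_w / √n), with s_w = √ln(1+CV²). The documents give no within-subject CV. I assume 25% (s_w = 0.246), with 20–30% as the range.

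| n | factor at 25% | range |
|---|---|---|
| 2 | 4.73 | 3.49–6.38 |
| 3 | 1.80 | 1.60–2.01 |
| 4 | 1.51 | 1.39–1.63 |
| 5 | 1.39 | 1.31–1.49 |
| 18 (pooled) | 1.15 | 1.12–1.19 |

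**2. t_max.** The widest finite signed-rank interval has confidence 1 − 2 × (1/2)^n: 75% at n=3, 87.5% at n=4, 93.75% at n=5. So 90% needs n ≥ 5. Since 18/5 = 3.6, at most 3 levels can hold five subjects at N=18 and at least 5 of 8 fail. Since 20/5 = 4, at least 4 fail at N=20. Counting splits within the enrolment limits (5–8 in Group A, 12–15 in Group B) gives the same maxima. Some levels can succeed: 13 subjects in Group B's three levels force at least one level to reach 5. With 6+12 spread equally at random within each group, 1.1 levels reach 5 on average.

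**3. Footnote.**

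*Log-SDs.* Protocol 1.2.4 gives 95% CIs for AUC after i.v. dosing with n = 18. Log-SD = ln(U/L)/2 × √18/2.110:
- selexipag (9.30, 13.38): 0.37
- ACT-333679 (11.42, 19.47): 0.54

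*Pass rate.* With one AUC per subject, SE(slope) = SD/√Sxx, where Sxx is the sum of squares of log dose. The CI includes 1 with a probability given by the noncentral t on n−2 df. As an example, put 1, 1, 1, 1, 2, 4, 4, 4 subjects at the eight levels. Then Sxx = 5.18, SE = 0.161 and 0.236, and the 90% half-widths are 1.746 × SE = 0.28 and 0.41. A true slope of 0.75 passes 56% and 73% of the time.

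With 6+12 at equal random spread (first figure selexipag, second ACT-333679), a slope of 0.7 passes about 42% and 64%, and a slope of 0.8 about 65% and 78%. A true slope of 1 passes 90%. Across extreme layouts the rate at slope 0.75 runs from 14% to 88%.

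**The case against.** - **The pooled row is already planned.** It stands in a key-deliverable shell, and Protocol 10.3.5 and SAP 8.2.2.1 can be read as planning both analyses. This largely stands: a reader might infer that the pooled ratio will be missing from the report, but that risk is low. SAP 12 lets outputs differ slightly from the mock-ups, which does not settle whether a model is run. The sample code is offered only as similar code, so its missing BY statement carries little weight.
- **Proportionality does bear on pooling.** This stands. From the cancellation in Table 6 a reader might infer that proportionality is irrelevant and that the pooled figure can be the main estimate with the check dropped. The SAP's statement on oral PK does not support that: if the oral slope is 1, an i.v. slope below 1 means the ratio is not constant. The protocol also ranks neither analysis above the other.
- **Some t_max intervals can be produced.** This stands. A reader might infer that the per-level analysis fails everywhere, but Group B levels with five or more subjects can deliver it.
- **The footnote sits in a mock table that also prints the slope, its SE and its CI.** The imprecision is therefore visible. The stated inference is still wrong, whatever its consequence.
- **The sizes rest on outside assumptions.** This stands for the CV, the dose spreads and the log-SDs, which come from a single-dose study of a different i.v. formulation in healthy men. It does not touch the n ≥ 5 limit, the cancellation at planned doses or the logic of the footnote.

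**Conclusion.** The concern holds for all three rules. The condition on the pooled model cannot be evaluated and conflicts with T_PK_MM. The exact 90% t_max interval is impossible in at least 5 of 8 levels at N=18 and at least 4 at N=20. The footnote rewards imprecision, passing a true slope of 0.7 about 42–64% of the time at 6+12 with equal spread, under the log-SDs assumed above.

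A reader might infer that the primary objective or an error rate is compromised. The documents do not support that. SAP 3.2 lists PK among the other objectives, SAP 8.2 makes all tests and intervals descriptive, and no margin or decision rule depends on these intervals. The point is worth correcting because the rules as written are undeliverable or unsupported and cheap to change.

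**What to change.** 1. **Pooled ratio.** Delete the conditional sentence in SAP 7.8.4.3. State there and in 8.2.2.1 that the pooled dose-normalised paired model is always fitted and shown with the per-level ratios, as T_PK_MM already lays out. State its assumption: a constant i.v./oral ratio across doses. Beside it, show the i.v. power-model slope with its 90% CI, and the i.v./oral ratio by dose group A/B (or against log dose) with 90% CI for AUCtau,ss and Cmax,ss. Do not claim that these verify constancy: at 6+12 and CV 25%, the A/B contrast has a 90% CI factor of about 1.36. Label the pooled row 200 µg oral / 225 µg i.v., to match SAP 7.8.3.1.
2. **t_max.** Report the pooled Hodges-Lehmann estimate from within-subject differences with the exact signed-rank 90% CI, in the T_PK_WIL layout. Keep the protocol's per-level analysis where n ≥ 5 and print n.e. elsewhere. Reword SAP 7.8.4.3 and 8.2.2.4, and record the change in SAP section 11.
3. **Proportionality.** Delete the T_PK_POW footnote, reword SAP 8.2.2.3 to match, and report the slope with its 90% CI.

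The cost is SAP wording, one row label, one footnote, a small added display for the ratio by dose group, and per-level rows in T_PK_WIL. What is given up is a yes/no statement on proportionality and t_max intervals at levels that could not have supported them.
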